# PROTOCOL SYNOPSIS

## Effects of structured skills training group in treatment of Attention Deficit Hyperactivity Disorder in adults

A growing number of adults are diagnosed with Attention-Deficit Hyperactivity Disorder, or ADHD. People with ADHD can have problems in paying attention, feeling restless or hyperactive and behaving impulsively. Pharmacological (drug) treatments are well established, but a significant number of patients does not respond well or experience adverse effects, which results in stopping the treatment. Furthermore many patients request for psychological treatment to help them with symptoms that are not resolved by simply taking drugs.

Structured group therapy has shown improvement of symptoms among patients with other psychiatric conditions. Although still inconclusive, some studies have indicated that structured skills training groups are beneficial for adult patients with ADHD in outpatient psychiatric units, reducing ADHD symptoms in people who remained stable regarding their medication status.

This study aim to investigate the potential effects of structured skills training groups in a clinically relevant but still controlled setting, and whether they help alleviate symptoms and improve quality of life for adult ADHD patients. This trial examines effects of Dialectical Behavioral Therapy-based group treatment (DBT-bGT) on the broader and clinically relevant executive functioning and emotional regulation in adults with ADHD

By use of a controlled design, adult patients with ADHD will be randomly assigned to receive either weekly DBT-bGT or treatment as usual (TAU) during 14 weeks therapy period. Subsequently, participants receiving TAU will also be offered the supplementary DBT-bGT. All participants will be reassessed at a follow-up visit six months after ended DBT-bGT.

Primary outcomes are the Behavior Rating Inventory of Executive Function (BRIEF-A) and the Difficulties in Emotion Regulation Scale (DERS). Secondary outcomes include self-reported ADHD-symptoms, depressive and anxiety symptoms, and quality of life assessments.

**Study Period:**

Recruitment start date December 2015  
Estimated recruitment end date 31/12/2016  
Anticipated study period: 2 years  
Estimated date of last patient completed: 31/12/2017

**Treatment Duration:**

Participants will be offered a 14 week manualized Dialectical Behavioral Therapy-based group treatment (DBT-bGT) or treatment as usual (TAU). After 14 weeks participants of the TAU group will be offered DBT-bGT as well.

**Objectives:**

The main objective for this trial is to investigate the potential effects of structured skills training groups in a clinically relevant but still controlled setting on broader outcomes including both symptomatic, functional and health related quality of life measures.

- Describing the effect of treatment by DBT-bGT on outcomes of the Behavior Rating Inventory of Executive Function (BRIEF-A) and the Difficulties in Emotion Regulation Scale (DERS) compared to treatment as usual
- Describing the effect of treatment by DBT-bGT on core symptoms of ADHD
- Describing the effect of treatment by DBT-bGT on other psychiatric symptoms and quality of life measurements

**Study Design:**

A multicentre Randomized-Controlled Trial, with a parallel group design; active treatment by a manualized Dialectical Behavioral Therapy-based group treatment (DBT-bGT) versus treatment as usual (TAU). Participants of the TAU groups eventually gets DBT and all participants are followed up 6 months after ended active treatment.

**Main Inclusion and Exclusion Criteria:**

- Diagnosis of ADHD assessed by a trained specialist clinician according to the Diagnostic and Statistical Manual of Mental Disorders, 4th. Edition (DSM-IV) persisting in adulthood
- Unmedicated or stably medicated with any ADHD-medication.
- Between 18 and 60 years of age (all groups).
- Exclusion criteria are any ongoing psychiatric disorders and/or

psychosocial factors considered to clearly interfere with the patients' ability to participate in the group, i.e., ongoing substance or alcohol abuse, psychotic disorder, major depressive or manic episode, and suicidal behavior; organic brain damage, neurological diseases causing mental handicap, intellectual disability ( $IQ \leq 70$ ), and pervasive developmental disorder.

- Sample Size:** Estimated 120 patients
- Efficacy Criteria:** Measures of changes in the defined outcome measures between groups and pre-post individually at follow-up.
- Safety Criteria:** In case of SAE (severe adverse events), patient will be considered for exclusion and indicated treatment will be administered immediately.

# INTRODUCTION

## 1.1. Background

Hyperkinetic disorder or attention-deficit hyperactivity disorder (ADHD) is the most common neurobiological developmental disorder in children and adolescents (Remschmidt, 2005). The incidence in Norway is assumed to be between 3-5% (Hdir, 2005). Studies estimate the prevalence of ADHD in the adult population to be about 2% (Philipsen, et al, 2010). Research shows that of those diagnosed as children, about 2/3 will have persistent functional difficulties in adulthood (Kooji et al., 2010). ADHD in adulthood has many serious consequences and is a risk factor for unfavorable socio-economic conditions, disease burden and intoxication, to name a few. Disabilities have been found to persist into old age. Up to 75% of the adult population with ADHD has also been shown to have other additional difficulties such as depression, abuse, difficulty sleeping, anxiety and low self-esteem. Studies show that a large number of patients, up to 50% of the adult population, do not benefit optimally from medication, and need other treatment instead or in addition to medication to cope with residual symptoms or comorbid conditions of their ADHD (Safren et al., 2005; Raman et al. 2015, Fredriksen et al., 2014).

Questions about ADHD currently make up a large proportion of referrals to child and adolescent psychiatry, and significant quality-improving work has been carried out within the health services with assessment, diagnosis and treatment of children and young people with ADHD. However, the mental health care for adults has not had a similar focus on ADHD. It is mainly the district psychiatric centers (DPS) that are responsible for the assessment and treatment of adults with ADHD. The contact with clinical environments and the user organization shows that the treatment options for adults with ADHD have their main focus on offering drug treatment. At the same time, there are studies that document that between 25 - 50% have a lack of continuity in their medication use after about one year (Aanonsen et al., 2005, Bejerot et al., 2010). In addition to drug treatment, there is little systematic knowledge about treatment options offered to this patient group in Norway.

## 1.2. Non-pharmacological treatment for ADHD in adults

A literature search in relation to non-drug treatment of adults with ADHD has revealed two relevant manuals; «Treatment that works; Managing your adult ADHD »(Safren et al., 2005) and« Psychotherapy for adults with ADHD »(Hesslinger et al.,2004; Hirvikoski et al., 2010). The former manual is based on cognitive-behavioral therapy, while "Psychotherapy for adults with ADHD" is a manual established over dialectical behavioral therapy (DBT). The manuals offer a method for dealing with symptoms (residual symptoms) where additional problems have been established, or where it is felt that drug treatment alone is not sufficient, - multimodal treatment (combination of drug and non-drug treatment). Both manuals have an introduction to psychoeducation. Such an approach is in accordance with, among other things, the national guide for the assessment and diagnosis of ADHD (IS-2062/2014), where psychoeducation is emphasized as an important element in treatment and follow-up. A recent user survey among adult patients with ADHD at four DPS in the Bergen area, showed that the most important predictor of satisfaction with the follow-up was whether the patients were satisfied with the information they had received about ADHD. Offering non-drug treatment was the single factor that most patients missed (Solberg et al., 2015, in press). This is also in accordance with the assignment document 2015, which emphasizes the importance of health trusts being able to offer both drug and non-drug treatment, where this is considered prudent.

### **1.3. Psychotherapy for adults with ADHD / Structured skills training group therapy**

The selected manual in this project is "Psychotherapy for adults with ADHD" (Hirvikoski, et al., 2010). The manual is based on DBT, which was originally developed for the treatment of personality disorders, but which has later come in a version adapted to the patient group of adults with ADHD. A basic principle in DBT is the balance between acceptance of the symptoms of ADHD and change (how to live best with the symptoms). In terms of content, the treatment consists of various components such as; psychoeducation, behavioral analysis, homework / skills training and mindfulness (exercises in mindful presence). The form of therapy has been developed to also take into account the emotional regulation difficulties and the effect they have on interpersonal relationships. According to the literature, this can be considered a core symptom of ADHD (Retz et al., 2012).

This manual has been developed with group treatment in mind (group of 7-9 participants). Experience from relatives' groups and contact with the patient association (ADHD Norway) indicates that follow-up in a group is preferable for several adults with ADHD, as you meet people in the same situation and can benefit from each other's experiences, while it can reduce perceived stigma related to the diagnosis. The treatment is given once a week, lasting 1-2 hours. There will be 14 treatment meetings, with homework between treatments in this structured skills training group therapy. Each group is led by 2 therapists.

## **2. STUDY OBJECTIVES**

The study wants to investigate the treatment effect of "Psychotherapy for adults with ADHD" given in groups, a manual made over DBT.

### **2.1. The hypotheses:**

- Adult patients with ADHD gain increased knowledge about ADHD
- Adult patients with ADHD experience increased coping ability in relation to their own condition and symptom regulation
- Adult patients with ADHD experience improvement in relation to self-reported additional symptoms / difficulties: emotional dysregulation, organizational difficulties, sleep, anxiety / depressive symptoms
- Adult patients experience improvement in relation to self-reported functional goals and quality of life

### **2.2. Endpoints**

Treatment effect will be investigated through mapping of symptoms of ADHD, anxiety and depression, as well as measures of functioning and quality of life before and after treatment. Registrations must be carried out before start-up (baseline) and after treatment (immediately and after 6 months) with the aim of evaluating the treatment effect.

- Behaviour Rating Inventory of Executive Functions (BRIEF)  
Change in executive function impairments

- Difficulties in Emotion Regulation Scale (DERS)  
Change in emotional regulation
- Adult ADHD Quality of Life Scale (AAQoL)  
Change in quality of life
- Adult ADHD self-report scale (ASRSv1.1), 18 items version  
Change in ADHD symptoms
- Beck Depression Inventory (BDI)  
Change in depressive symptoms
- Beck Anxiety Inventory (BAI)  
Change in anxiety symptoms
- Weiss Functional Impairment Rating Scale, self-report (WIFRS)  
Change in functional impairments
- Global Assessment of functioning (GAF)  
Change in global symptoms and functioning

### **3. STUDY POPULATION**

#### **3.1. Selection of study population**

Participants with ADHD diagnosis (according to DSM-IV criteria) will be recruited from the psychiatric specialist health services, mainly District Psychiatric Centres but also from privately practicing specialists in psychiatry / clinical psychology in the region of the centres taking part. Participation in the study is voluntary and consent-based. Information about the study will be announced to clinicians in the specialist health service and private practitioners via email and through the hospitals' websites, as well as distributed to relevant sections and professionals in the relevant hospitals in Helse Vest and Helse Sør-Øst.

#### **3.2. Number of participants and intervention**

Inclusion will progress until about 120 participants are enrolled into this trial. The participants who will be randomized into two groups; and allocated to either:

1. Group 1 (G1) with start of weekly treatment in active structured skills training group therapy lasting for 14 weeks, following the Norwegian translation of the Swedish version of the ADHD skills training manual/workbook (Hirvikoski 2011; Morgensterns 2015) based on an adaption of Marsha Linehan's dialectical behavior therapy (DBT) for borderline personality disorder. The groups embrace 7 - 10 participants, and two group leaders trained in group therapy, cognitive behavioral treatment or DBT. Each session contains an initial short repetition and feedback on the previous session, followed by review of the homework during the first hour. After a break, a new topic with exercises and homework for the following week is introduced.

2. Group 2 (G2) with treatment as usual/clinical management for the first 14 weeks, followed by delayed admission to the active intervention of structured skills training group therapy (partial cross-over).

##### **3.2.1. All participants**

For eligibility the prospective participants at screening prior to receiving the study intervention must meet all of the following conditions:

- Clinically diagnosed with ADHD according to DSM-IV. Diagnostic assessment is part of standard diagnostic procedures at the clinics, which include confirmatory assessment by a specialist in psychiatry or psychology
- On stable treatment with ADHD medication or off medication.
- Must be between the ages of 18 and 60.
- Signed informed consent and expected cooperation of the patients for the intervention and the questionnaires must be obtained and documented according to International Conference on Harmonization, Good Clinical Practice and national/local regulations.

### **3.3. Exclusion criteria**

[figure not shown]
Any participant (from either of the three groups) will be excluded from the study if ongoing psychiatric disorders and/or psychosocial factors are considered to clearly interfere with the patients' motivation or ability to participate in the group therapy, and if they meet any of the following criteria:

- Any psychotic disorder
- Recently suicidal behaviour
- Substance or alcohol abuse or dependence within three months prior to screening for inclusion
- Pervasive developmental disorder
- Intellectual disability
- Seizures or any neurological diseases causing mental handicap

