### **6.3. Enrollment of patients**

Treating clinicians will ask patients whether they are interested in participation as they meet for regular appointment. Project therapists will evaluate patient eligibility and be responsible for acquiring informed consent (for either DBT, or TAU). Patients will then be given oral and written information, and asked to give permission for one of the contributing researchers to contact them.

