### **6.4. Criteria for patient discontinuation**

Patients may be discontinued from study treatment and assessments at any time. Specific reasons for discontinuing a patient for this study are:

- Voluntary discontinuation by the patient who is at any time free to discontinue his/her participation in the study, without prejudice to further treatment.
- Safety reason as judged by the Principal Investigator.
- Incorrect enrollment (i.e. the patient does not meet the required inclusion/exclusion criteria for the study)
- Related Serious Adverse Event

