## **10.2. Randomisation**

Participants are randomly allocated (ratio 1:1) to either the active DBT-bGT or the control TAU condition by a blinded lottery procedure at each site. This manual procedure of randomization method is suitable to randomize participants into groups that result in equal sample sizes, and is used to ensure a balance in sample size across groups over time.

At each site, clinicians are recruiting patients for the study. Patients who consent to participate are assigned a unique number by the study administrator at the site, entering it to a key code list. When the list is fully subscribed with a sufficient number of participants to form two groups, all the numbers are written on a folded piece of paper, and placed in a container. Then, under supervision and by a lottery procedure, one number at a time is drawn by an independent person every second time to the DBTgroup and the TAU-goup respectively. The draw takes place blindly for the participant and the person who draws and the monitor. Afterwards, when all the numbers have been drawn and assigned to their group, are the numbers with corresponding name and group announced so that the participants get to know which group they shall belong to in the study.

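### Section 6.4 lets a randomised patient be dropped from assessments for incorrect enrolment, and section 3.3 sets no time limit on the eligibility criteria this refers to

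*Protocol*

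**What the plan says.** **Entry.** Section 3.2.1 ties inclusion to screening: "For eligibility the prospective participants at screening prior to receiving the study intervention must meet all of the following conditions". Section 6.3 gives the judgement to the treating side of the project: "Project therapists will evaluate patient eligibility and be responsible for acquiring informed consent (for either DBT, or TAU".

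**Exclusion.** Section 3.3 changes the subject from prospective participants to participants: "Any participant (from either of the three groups) will be excluded from the study if ongoing psychiatric disorders and/or psychosocial factors are considered to clearly". The rest of that sentence names the effect and adds a second requirement: "interfere with the patients' motivation or ability to participate in the group therapy, and if they meet any of the following criteria". Six bulleted conditions follow. Only one is dated: "Substance or alcohol abuse or dependence within three months prior to screening for inclusion". The synopsis words the test differently. It refers to ability only, offers its conditions as an explanation of the interference and not as a second requirement, and has a different list (for example, it names a major depressive or manic episode, which 3.3 does not).

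**Draw.** Section 10.2 holds the lottery after consent, at this point: "When the list is fully subscribed with a sufficient number of participants to form two groups". Allocation is announced afterwards. Sections 3.2 and 10.2 describe two groups.

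**After the draw.** Section 6.4 allows discontinuation from both treatment and assessments at any time. Its listed reasons include: "Incorrect enrollment (i.e. the patient does not meet the required inclusion/exclusion criteria for the study". Section 6.4.1 provides continued clinical care for those withdrawn but says nothing of continued questionnaires. Section 10.3 restricts each analysis to participants who responded.

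**The concern.** A randomised comparison is protected only if those drawn stay in it, or leave it for reasons unrelated to arm. Here a finding made after the draw, that someone did not meet the criteria, is a stated ground for ending data collection on that person. The criteria rest partly on judgement (clear interference with taking part in the group), carry no explicit cut-off at the draw, and differ between the synopsis and 3.3. Whether someone counts as incorrectly enrolled can therefore depend on which text is read and on who looks.

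The two arms are not observed equally. Under section 5.1 a DBT-bGT patient attends 14 weekly two-hour sessions, each followed by individual coaching. A TAU patient has unstandardised clinical management (5.2), and the next stated study assessment is at week 14 (7.1). If ineligibility is noticed more often in the arm that is watched more closely, and those removed would have done worse than average, the remaining DBT-bGT patients look better than the arm that was drawn. An analysis plan cannot repair this, because the questionnaires would not have been collected.

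**Working it through.** **1. Is 3.3 a rule for after the draw?** The literal words reach any participant in any group, without a time point. Four things point to entry instead: the section heading, the screening wording in 3.2.1 just before it, the substance item dated from screening, and the order of consent and draw in 6.3 and 10.2. The reference to three groups matches nothing in this design, so it is no evidence of intent. The best reading is a badly worded entry criterion.

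**2. What does 3.3 require?** Two conditions joined by *and*: psychiatric or psychosocial factors that clearly interfere, and a listed condition. Low motivation alone does not qualify.

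**3. Can a drawn patient leave the comparison?** Yes, whichever way 3.3 is read. Section 6.4 permits assessments to stop for incorrect enrolment and sets no limit at the draw. Section 6.4.1 does not restore them. Section 10.3 then omits the patient. The word used in 6.4 is *may*, so this is permitted and not required.

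**4. The plan's own figures (10.1, with the two-sided 5% level from 10.3).** Difference 10, SD 15, power 0.90, allocation 1:1.
- n = 2 × [15 × (1.960 + 1.282) / 10]² = 47.3, so 48 per group, in line with the stated figure of about 50.
- 48 / (1 − 0.20) = 60 per group, 120 in total, as stated.

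**5. Illustrative size.** The following are assumptions, not in the protocol: 60 drawn per arm, a fraction p removed from DBT-bGT only, and those removed doing 0.5 to 1.0 SD worse (7.5 to 15 points).

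*Gap D measured against the whole arm's mean:* shift = p × D / (1 − p).

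| p (patients) | D = 7.5 | D = 15 |
|---|---|---|
| 0.05 (3 of 60) | 0.39 | 0.79 |
| 0.10 (6 of 60) | 0.83 | 1.67 |

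*Gap measured against those kept:* shift = p × D. This gives 0.375 to 0.75 at 5% and 0.75 to 1.5 at 10%.

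Across both conventions the range is about 0.4 to 1.7 points, or 4% to 17% of the planned 10.

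*Type I error with no true effect, second convention:* SE = 15 × √(1/60 + 1/n₁), and error = Φ(−1.96 + b/SE) + Φ(−1.96 − b/SE), where b is the shift.
- p = 0.05: n₁ = 57, SE = 2.774, error 5.2% to 5.8%.
- p = 0.10: n₁ = 54, SE = 2.814, error 5.8% to 8.3%.

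*Power at a true difference of 10, ignoring bias:* 0.9546 at 60 v 60 and 0.9445 at 54 v 60. The issue is bias, not sample size.

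**The case against.** The strongest reply is that 3.3 is an entry criterion with a drafting slip, and that incorrect enrolment in 6.4 means a fact already true at entry, which can come to light in either arm. Most of the listed conditions are long-standing diagnoses that group attendance would not reveal. TAU patients remain under clinical care, where such conditions can also be noticed. Project therapists judge eligibility before allocation exists, and the draw is blind. How ineligible randomised patients are analysed is commonly left to the analysis plan, which is not at hand.

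Much of this stands. A reader might infer that the protocol lets therapists remove poorly motivated patients after the draw, mainly from DBT-bGT. The documents do not support that. Motivation alone is not a ground, no section gives therapists a power of exclusion after the draw, and no section reports or predicts removals by arm.

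Two things survive. First, some listed conditions (psychotic disorder, recent suicidal behaviour) are undated in 3.3 and may emerge or be detected after the draw, so closer contact in one arm can still matter. Second, stopping assessments is a conduct rule written into this protocol, and 10.3 already fixes a responders-only analysis. Neither is a matter left open for a later plan.

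**Conclusion.** The point holds in a limited form. Section 3.3 is faulty wording: no time point, a group count that contradicts the design, and a test that disagrees with the synopsis. The substantive weakness is in 6.4, which, together with 10.3, permits a randomised patient judged incorrectly enrolled to drop out of the comparison, at the discretion of staff to whom allocation may be known.

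Differential detection in DBT-bGT is a plausible inference from the unequal contact during the 14 weeks. Its direction and size are not documented. The 0.4 to 1.7 points are correct arithmetic on assumed removal rates, an assumed deficit and no removals from TAU; they show scale and are not a forecast. If removals were rare or equal in kind and number across arms, the effect would be negligible. The planned sample size reproduces and is unaffected. The change is worth making because it is cheap and closes a route to bias that analysis cannot close later.

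**What to change.** - **Section 3.3:** state that the eligibility criteria are applied only before the draw, and delete the phrase about three groups. Reconcile the section with the synopsis on three points: whether a listed condition is required in addition to interference, whether motivation counts, and which conditions are listed. Which version is right is for the investigators to settle.
- **Section 6.4:** remove incorrect enrolment as a reason to stop assessments. Everyone drawn is asked to complete the week-14 and follow-up questionnaires and is analysed in the drawn arm. Patients remain free to withdraw, and clinical decisions to stop therapy are unaffected.
- **Optional:** a dated eligibility recheck shortly before each lottery, since the list must first fill to two groups (14 to 20 people at the 7 to 10 per group in section 3.2) and status may change while people wait.

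The cost is a wording amendment and a few extra questionnaires. A few ineligible patients will stay in the analysis and may slightly dilute the effect. The optional recheck could delay a draw a little if someone leaves the list.
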